11.2 Analysis of Secondary Objective

There are several secondary outcomes of interest in this study. Most of these are measured on a continuous scale (i.e., quality of life by QLQ-C15-PAL, Patient satisfaction with cancer care, perceived stress scale) and thus will be compared between groups using 2-sample t-tests. In addition, the variable for pain response is categorical rather than continuous and will be compared at 3-months between groups using a Fisher's exact test. Patients categorized as Complete or Partial Responders will be compared with those categorized as stable or worsening pain responders.

Groups will also be compared to determine whether there are any differences in the number or severity of toxicities. When comparing severity of toxicities between groups, chi-square tests will be examined. The Cochran-Armitage trend test (in SAS Proc Freq) can be used to determine if there is evidence a trend in severity of toxicities when comparing groups.

In addition to the primary and secondary analyses described above, analyses will be performed that examine whether there are associations between quality of life, patient satisfaction and perceived stress measures and treatment outcome (re-treatment rates or amount of pain relief). In these

analyses, the outcome will be either re-treatment (yes/no) or amount of pain and predictors will include treatment arm, patient level measure and the treatment by patient level measure (i.e., QLQ-C15-PAL) interaction. For these analyses, either multiple logistic regression (for binary outcomes) models or analysis of covariance (ANCOVA) models for continuous outcomes will be used.

In these multiple logistic regression or ANCOVA models additional characteristics such as gender, whether the patient has weight-bearing (yes/no), ECOG performance status, number of lesions, or biophosphonates will also be considered as covariates in the models.

For the exploratory outcome of examining the association between the use of a bone strengthening agent with pain relief, narcotic use and re-treatment rates either two-sample t-tests (if pain is measured on a continuous scale) or Fisher's exact tests (for categorical measures) will be used. In addition multiple logistic regression or ANCOVA models will be fit to look at the an outcome (i.e., pain relief yes/no) and the impact of bone strengthening agents (yes/no), number of metastases (one/more than one), treatment group (8/1 or 8/2) and the treatment by bone strengthening interaction.

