2.2 Secondary Objectives

- 2.2.1 To determine whether 8 Gy x 2 fractions provides superior pain at 3 and 6 months post-treatment completion compared to 8 Gy x 1 fraction in solid tumor patients with bone metastases.
- 2.2.2 To determine whether 8 Gy x 2 fractions is associated with improved quality of life at 3 and 6 months post-treatment completion compared to 8 Gy x 1 fraction in solid tumor patients with bone metastases.
- 2.2.3 To determine if 8 Gy x 2 fractions is associated with increased toxicity.
- 2.2.4 To correlate patient satisfaction, perceived stress, and social support assessed via self-reported outcomes with treatment outcomes.

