5.2 Secondary Outcomes

- 5.2.1 Pain, on a 0-10 scale, and narcotic use, in daily oral morphine equivalents, by treatment arm assessed at 3 and 6 months post-treatment completion.
- 5.2.2 Quality of life by treatment arm, assessed by QLQ-C15-PAL at 3 and 6 months post-treatment completion.
- 5.2.3 Toxicity by treatment arm, assessed by CTCAE version 4.0.
- 5.2.4 Association between patient satisfaction, perceived stress, and social support assessed via self-reported surveys and treatment outcomes.

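### Section 11.2 compares quality of life by t-test with no stated use of the baseline score already collected; ANCOVA would be more precise, and the arm tests of pain score and morphine equivalents should be named

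*Combined protocol and SAP*

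**What the plan says.** **Quality of life.** Objective 2.2.2 asks whether two fractions "is associated with improved quality of life at 3 and 6 months post-treatment completion", and outcome 5.2.2 sets QLQ-C15-PAL at the same two times. Section 4.3 and the schedule in 6.1 collect the questionnaire at baseline, 3 and 6 months. On the secondary outcomes section 11.2 says "Most of these are measured on a continuous scale (i.e., quality of life by QLQ-C15-PAL, Patient satisfaction with cancer care, perceived stress scale"), and that they "thus will be compared between groups using 2-sample t-tests". It attaches no baseline term, change score or time point to that sentence.

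**Pain.** Objective 2.2.1 asks whether two fractions "provides superior pain at 3 and 6 months post-treatment completion". Outcome 5.2.1 is "Pain, on a 0-10 scale, and narcotic use, in daily oral morphine equivalents, by treatment arm assessed at 3 and 6 months post-treatment completion". In section 11.2, "the variable for pain response is categorical rather than continuous and will be compared at 3-months between groups" by Fisher's exact test. The section also describes logistic and ANCOVA association models. Their outcome is re-treatment or amount of pain, and their predictors are arm, a patient-level measure and the interaction of the two. The covariates given as examples are gender, weight-bearing site, ECOG status, number of lesions and bisphosphonates. For the exploratory comparison by bone-strengthening agent, the text offers "either two-sample t-tests (if pain is measured on a continuous scale"), and a model of "an outcome (i.e., pain relief yes/no") that includes treatment group.

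**The concern.** Quality of life at follow-up usually depends partly on quality of life at entry. A comparison of follow-up scores that ignores the entry score leaves that variation in the error term. With 51 patients per arm before losses, precision matters, and here it can be had from data the trial already collects.

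The pain text raises a related but smaller question. The two measures in 5.2.1, each at 3 and 6 months, are the stated pain outcomes by arm, and section 11.2 does not say explicitly which test applies to them or when. Criterion 3.1.5 admits patients with pain of 5 or more, and also patients with pain below 5 on at least 60 mg of morphine per day. Both measures therefore vary widely at entry, and the handling of baseline matters for them as well.

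**Working it through.** **1. The plan's own figures.** Section 11.2 gives no power figure for any secondary outcome. The only sizing is for the primary: 51 per arm, 20% lost to follow-up, competing-risk incidence 0.20 and event incidence 0.18 and 0.10. The software output in 11.6 places both incidences at 3 months. The total hazards are then -ln(1 - 0.18 - 0.20)/3 = 0.1593 (control) and -ln(1 - 0.10 - 0.20)/3 = 0.1189 (treatment). The competing parts are 0.1593 × 0.20/0.38 = 0.0839 and 0.1189 × 0.20/0.30 = 0.0793, which match the printed output.

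**2. Evaluable patients per arm at 6 months.**
- Loss to follow-up only: 51 × 0.8 = 40.8, about 41.
- Loss plus a competing risk of 0.20 at 6 months, as section 11.3 words it: 51 × 0.8 × 0.8 = 32.6, about 33.
- Loss plus the hazards in step 1: 6-month competing incidence is (0.20/0.38)(1 - 0.62²) = 0.324 and (0.20/0.30)(1 - 0.70²) = 0.340. This gives 51 × 0.8 × 0.676 = 27.6 and 51 × 0.8 × 0.660 = 26.9; 27 is used as the low end.

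**3. Variance.** Let r be the correlation of baseline with follow-up (assumed). The ANCOVA variance relative to a raw-score t-test is 1 - r², which is 0.91, 0.75 and 0.64 at r = 0.3, 0.5 and 0.6. So 33 per arm with ANCOVA is worth 33/(1 - r²) = 36, 44 and 52 per arm with the t-test.

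**4. Power for an assumed difference of 0.5 SD.** Noncentral t with noncentrality d√(n/2). The t-test uses d = 0.5 and 2n - 2 degrees of freedom; ANCOVA uses 0.5/√(1 - r²) and 2n - 3.

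| Alpha | n per arm | t-test | ANCOVA, r = 0.3 / 0.5 / 0.6 |
|---|---|---|---|
| two-sided 0.05 | 27 | 43.8% | 47.2 / 54.8 / 61.5% |
| two-sided 0.05 | 33 | 51.6% | 55.4 / 63.7 / 70.5% |
| two-sided 0.05 | 41 | 60.9% | 65.0 / 73.3 / 79.8% |
| one-sided 0.2 | 27 | 83.9% | 85.9 / 89.8 / 92.6% |
| one-sided 0.2 | 33 | 88.2% | 90.0 / 93.3 / 95.4% |
| one-sided 0.2 | 41 | 92.2% | 93.7 / 96.1 / 97.6% |

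The gain runs from about 3 to 19 points in the first block and about 2 to 9 in the second.

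**5. If the t-test is meant on change scores.** The change-score variance relative to raw is 2(1 - r), so ANCOVA relative to change is (1 - r²)/(2(1 - r)) = (1 + r)/2 = 0.65, 0.75 and 0.80. ANCOVA is the more precise on that reading too.

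**6. Missing baselines.** Footnote h in 6.1 does not require the questionnaire for registration. If 9% had no baseline score and were dropped, 33 would become 33 × 0.91 = 30. At r = 0.3 and two-sided 0.05, power would be 51.5% against 51.6% for the t-test, so the gain is lost unless those patients are kept.

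**7. The pain text, side by side.** Outcome 5.2.1 implies four arm comparisons: two measures at two times. None is named explicitly in 11.2. The association models join arm with amount of pain, but they carry an interaction and state no time point, so they are not a simple arm comparison. Narcotic use appears in the analysis text only in the comparison by bone-strengthening agent.

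**The case against.** The strongest reply on quality of life is that the t-test is sound under randomisation and that ANCOVA is a preference about efficiency. The first half stands. A reader might infer that the planned test is biased or wrong; it is not. The size of the gain is also uncertain. At one-sided 0.2, the only alpha the plan states and that for the primary, assumed power is already 84% to 92%.

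On pain, three stronger readings are tempting and do not hold.

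- That pain score and narcotic use have no planned arm analysis. Section 11.2 says that most secondary outcomes are continuous and then contrasts pain response as categorical, so the t-test sentence may well be meant to cover both. Its list also leaves out social support, which suggests that it is not exhaustive, and the abbreviation before it is used loosely elsewhere in 11.2. The association models also contain arm and amount of pain, and their covariate list is open.
- That the planned pain analysis ignores earlier values. The 3-month Fisher test is on response, and section 7.1 builds response from changes in the pain score and in morphine equivalents.
- That a promised 6-month response test is missing. Objective 2.2.1 speaks of pain at 6 months and 5.2.1 lists score and narcotic use; neither promises a response comparison then.

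What remains on pain is that the arm test and its time points are left to inference, with no dedicated arm test of pain explicitly named at 6 months.

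**Conclusion.** The quality-of-life point holds as a matter of precision, not validity. If the t-test is on raw follow-up scores, ANCOVA lowers the variance by 9% to 36%, worth roughly 3 to 19 points of power at two-sided 0.05 or 2 to 9 at one-sided 0.2. This rests on an assumed 0.5 SD difference, correlations of 0.3 to 0.6, 27 to 41 evaluable per arm and baselines kept for everyone analysed.

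The pain point is a secondary clarification and has no power figure: the two measures in 5.2.1 need a named test with time points. The primary analysis is not affected.

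A reader might also infer that the timing of the baseline questionnaire, which footnote h allows after randomisation but before treatment, is a fault. It is not one for the t-test as planned. It only becomes worth tightening once the score is a covariate.

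**What to change.** In section 11.2:

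- Replace the t-test for QLQ-C15-PAL with ANCOVA at 3 and at 6 months, with arm and the baseline value of the same measure as terms.
- Name the same model for the arm comparison of the 0-10 pain score and of daily morphine equivalents at 3 and 6 months, each with its own baseline, using a log or rank-based version if the data are skewed.
- Keep patients with a missing baseline by a simple imputation of that baseline, for example the mean over both arms combined.

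Optional: add a Fisher test of pain response at 6 months, or say that response is compared at 3 months only. Also optional: have the baseline QLQ-C15-PAL completed before randomisation, by separating the questionnaire from the blood collection in footnote h. Since section 4.1 requires treatment to begin within 14 days of registration, this would bring the questionnaire forward by at most about 14 days.

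The cost is a few sentences of SAP wording and slightly more analysis work. The schedule in 6.1 already collects the pain scale, bone-pain medications and questionnaires at baseline, 3 and 6 months, so no new data are needed.

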1.0 Introduction and Background

Bone metastases are not only the most common cause of cancer-related pain, but palliative radiotherapy is prescribed most frequently to relieve symptoms. External beam radiotherapy (EBRT) is a well-established and efficacious method of palliating painful bone metastases (1). Numerous randomized trials have evaluated the potential benefits of certain dose fractionations of EBRT (1-7), yet controversy remains over the optimal treatment schedule. For example, RTOG 97-14 randomized 898 patients with breast or prostate cancer to receive 8 Gy in 1 fraction or 30 Gy in 10 fractions. There was no significant difference in complete or partial pain relief at 3 months. Patients in the single dose group had a significantly higher retreatment rate at 3 months (18% vs. 9%) but a statistically lower toxicity rate (10% vs 17%) (8). An economic analysis of this trial calculated quality-adjusted life year survival to be 7.3 months vs 9.5 months in the two treatment arms. The authors concluded that single fraction was less expensive and more cost-effective (9). Chow et al conducted a systematic review and meta-analysis of randomized palliative radiotherapy trials comparing single fractions to multiple fractions. Twenty-five randomized trials were identified with no significant differences in pain response rates. The likelihood of re-treatment was 2.6-fold higher (95% CI, 1.92-3.47; $P < 0.00001$) in single fraction EBRT arm patients (10).

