11.3 Power and Sample Size

Power calculations were performed using PASS 13. When accounting for competing risks, a one-sided logrank test with an overall sample size of 102 subjects (51 in the control group and 51 in the treatment group) achieves 80% power at a 0.2 significance level to detect a hazard ratio of 0.5251. The study is expected to last for 42 months with an accrual (entry) time of 36 months and a follow-up time of 6 months after the last patient is accrued. The cumulative incidence proportions at time 3 months for the event of interest are 0.18 in the control group (8/1) and 0.10 in the treatment group (8/2). The cumulative incidence proportions at time 6 months for the competing risk factors are 0.20 in the control group and 0.20 in the treatment group. The proportion of subjects lost to follow-up during the entire study is conservatively estimated at 0.2.

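### Toxicity is analysed only by significance tests with no stated level, estimate or bound, so a non-significant result could not show that 8 Gy x 2 does not increase toxicity

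*Combined protocol and SAP*

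**What the plan says.** Section 2.2 sets a directional safety objective: "To determine if 8 Gy x 2 fractions is associated with increased toxicity". The matching outcome in section 5.2 is "Toxicity by treatment arm, assessed by CTCAE version 4.0".

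The between-arm analysis is in section 11.2. It opens with "Groups will also be compared to determine whether there are any differences in the number or severity of toxicities" and then names the methods: "When comparing severity of toxicities between groups, chi-square tests will be examined", and "The Cochran-Armitage trend test (in SAS Proc Freq) can be used to determine if there is evidence a trend in severity of toxicities". No level or sidedness is attached to either test. Neither that section nor any other gives an estimated difference, a confidence interval, an upper bound, a margin or a power figure for toxicity.

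The only level in the documents belongs to the primary endpoint. Section 11.3 describes a one-sided log-rank test on re-treatment with an "overall sample size of 102 subjects (51 in the control group and 51 in the treatment group" that "achieves 80% power at a 0.2 significance level to detect a hazard ratio of 0.5251". The interim rule in section 11.6 also concerns re-treatment alone. Section 8.3 and Appendix D provide for event-by-event review of serious adverse events by the DSMC.

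**The concern.** The objective can be answered yes or no. A significant test can support yes. Nothing planned can support no: a non-significant test at this sample size is compatible with no increase and with a sizeable one, and the plan specifies no other output that would tell them apart.

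This matters because the experimental arm has twice the total dose of the control arm, and section 4.3 singles out serious late events for follow-up (fistula, bowel obstruction, in-field fracture, spinal cord damage). Any conclusion on two fractions will weigh fewer re-treatments against toxicity, so the reader needs to know how large an increase the data leave open. Leaving the level unstated adds to the difficulty, because the chance of flagging a given increase depends heavily on a choice the plan has not fixed.

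**Working it through.** **1. The plan's own power figure.** The printed PASS output in section 11.6 gives 27.5 events, hazard ratio 0.5251, one-sided alpha 0.2 and power 0.80195. With equal allocation, power = Φ(√E × 0.5 × |ln HR| − z), where z = 0.8416. Here √27.5 × 0.5 × |ln 0.5251| = 1.689, and Φ(1.689 − 0.842) = 0.802. The figure reproduces. It concerns re-treatment; there is no toxicity figure to reproduce.

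**2. Inputs for the toxicity illustration.**
- 51 patients per arm (section 11.3). About 41 per arm remain if the 20% loss in that section applies (0.8 × 51 = 40.8).
- Yardstick rates of 10% and 17% (section 1.0). They are the cited trial's rates for 8 Gy x 1 and 30 Gy in 10 fractions. Neither is a rate for 8 Gy x 2.
- Assumption: a binary endpoint (any toxicity, yes/no) and an uncorrected chi-square.
- Assumption: the test level. None is stated, so a range is shown.

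**3. Chance of missing 10% versus 17%.** The statistic is z = (p₂ − p₁) / √[2 p̄(1 − p̄)/n]. Both binomials were enumerated exactly, and the probability of not rejecting was summed. The normal approximation is a cross-check: power = Φ{(0.07 − z_α × 0.0677)/0.0673}, where 0.0677 = √(2 × 0.135 × 0.865/51) and 0.0673 = √[(0.10 × 0.90 + 0.17 × 0.83)/51].

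| Level assumed | Missed, exact, 51 per arm | Missed, normal approx. |
|---|---|---|
| one-sided 0.2 | 42.2% | 42.3% |
| two-sided 0.2 | 58.2% | 59.8% |
| one-sided 0.05 | 73.5% | 73.0% |
| two-sided 0.05 | 82.9% | 82.4% |

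At 41 per arm the two ends become 44.5% and 84.1%. A continuity-corrected or Fisher test at two-sided 0.05 misses about 89 to 90% at 51 per arm.

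**4. What the same data say as an estimate.** These bounds need no choice of test level, only the confidence level shown. Newcombe's upper bound is d + √[(u₂ − p₂)² + (p₁ − l₁)²], where l and u are Wilson limits with z = 1.645.
- *Identical counts, 5/51 and 5/51.* p = 0.0980, Wilson limits 0.0485 and 0.1880, d = 0. Upper bound = √[(0.1880 − 0.0980)² + (0.0980 − 0.0485)²] = √(0.00810 + 0.00245) = 0.103, or about +10 points. A 7-point excess is not excluded even when the arms look the same.
- *9/51 on 8/2 and 5/51 on 8/1.* d = 4/51 = 0.078, upper bound +19.3 points. The pooled z is 1.151, so p = 0.25 two-sided and 0.125 one-sided. The same data are non-significant at two-sided 0.05 and significant at one-sided 0.2.

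**The case against.** The strongest objection is to the size of the problem. The miss rate of about 83% depends on a two-sided 5% level that the documents do not set. The objective is directional and the only level in the documents is one-sided 0.2. At that level the miss rate for the yardstick is about 42%, and the 9/51 versus 5/51 result would be flagged as increased toxicity. This stands: no single miss rate can be attributed to the plan, only a range with the level stated.

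A reader might also infer that benefit will be judged at 20% and harm at 5%, or that a non-significant result will be reported as no difference. The documents say neither. The first needs a toxicity level that is not given. The second is a risk left open by a test-only plan, not something the plan announces.

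Three further points have weight. The 17% belongs to a different schedule. Section 11.2 speaks of the number and severity of toxicities, and a trend test across grades could have different power, which cannot be computed because no grade distribution is given. Weak secondary safety comparisons are also normal in a randomised phase II trial, and 11.2 specifies no intervals for its other secondary tests either.

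None of this supplies the missing output. DSMC review works case by case and gives no between-arm estimate. Nothing in the plan forbids reporting rates and intervals, but nothing requires it. The bounds in step 4 rest on neither a test level nor the 17%.

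**Conclusion.** The concern holds in a limited form. Section 11.2 addresses objective 2.2.3 only through tests without a stated level, and a non-significant result from them could not show that two fractions do not increase toxicity. For a binary endpoint and an uncorrected chi-square at 51 per arm, a rise from 10% to 17% would be missed between about 42% of the time (one-sided 0.2) and 83% (two-sided 0.05). Even equal observed counts of 5/51 leave an increase of about 10 points open.

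The range rests on borrowed yardstick rates, an assumed endpoint and assumed levels; the absence of an estimate or bound rests on the text alone. The primary design and its power are unaffected. This is an inexpensive improvement to the analysis and reporting of a secondary objective.

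**What to change.** In section 11.2, make the toxicity result an estimate:
- For each arm, report the proportion of patients with toxicity at grade thresholds that the team names before the data are examined, and the proportion with each focused late event listed in section 4.3.
- For each, report the difference (8/2 minus 8/1) with a one-sided 95% upper bound, for example by Newcombe's method.
- Keep the chi-square and trend tests as descriptive.
- State that the safety conclusion rests on the largest increase the data do not exclude, and that a non-significant test will not be presented as absence of increased toxicity.

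The data are already collected on the Appendix I logs, so no extra patients or visits are needed. The cost is a paragraph of SAP text, one extra table, and a less favourable safety statement, because the bound will be wide at this sample size. That width is the information a later trial needs.

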4.0 Methods

4.1 Study Design

We will use a prospective randomized study design for recruiting patients with painful bone metastasis at the CCCWFU. Pain will be assessed prior to randomization. Patients will be randomized between 1 or 2 fractions of 8 Gy. The randomization will occur after registration; patients will be randomized equally between the two treatment arms. Treatment needs to begin within 14 days of registration. All baseline data needs to be collected before treatment. Quality control, such as valid values, range checks and between-variable consistency will be performed at time of data entry. Data will be kept secure with password protection.

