Appendix I – CCCWFU 01416 Adverse Event (AE) Log

PI: _____	PID: _____	MRN: _____									
Start Date: _____	End Date: _____	Time Point (choose one)	1 month								
Adverse Event CTC Term	Value (-5 if nonnumeric)	Grade (0-5) per CTC	Start Date	Attribution 1=Related 2=Probably 3=Possible 4=Unlikely 5=Unrelated	Treating MD Initials/Date	End Date	Expected 1=Yes 0=No	Serious Adverse Event (SAE) 1=Yes 0=No	Dose Limiting Toxicity (DLT) 1=Yes 0=No	Action Taken 1=None 2=Tx withheld 3=Tx D/C 4=Tx adjusted 5=Other	Reportable? (1-IRB 2-STRC, 3-FDA 4-Sponsor)
Nausea							1				
Vomiting							1				
Diarrhea							1				
Skin erythema							1				
alopecia							1				
esophagitis							1				
myelosuppression							1				
Urinary urgency							1				
Urinary frequency							1				
pneumonitis							1				
Pain (increased from baseline)											

Serious Adverse Event: Hospitalization; Disability; Birth Defect; Life-threatening; Death.

CTCAE Version 4 - http://evs.nci.nih.gov/ftp1/CTCAE/CTCAE_4.03_2010-06-14_QuickReference_8.5x11.pdf

CCCWU # 01416

Patient ID: _____ Date of completion: _____

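### The plan commits to chi-square tests for toxicity severity, leaves the ordered trend test optional, and does not say which one decides

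*Combined protocol and SAP*

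**What the plan says.** Objective 2.2.3 is directional: "To determine if 8 Gy x 2 fractions is associated with increased toxicity". Outcome 5.2.3 is toxicity by arm under CTCAE version 4.0, and the log in Appendix I records it on an ordered scale, "Grade (0-5) per CTC".

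Section 11.2 plans to compare both how many toxicities occur and how severe they are. For severity it says "When comparing severity of toxicities between groups, chi-square tests will be examined". It then adds: "The Cochran-Armitage trend test (in SAS Proc Freq) can be used to determine if there is evidence a trend in severity of toxicities". The first sentence is a commitment and the second a permission.

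The section does not say which result decides, how grades are grouped, whether the unit is a patient's worst grade or each adverse event term, what alpha or sidedness applies, or what happens when cells are small. No power is given for toxicity. By contrast, section 11.2 names Fisher's exact test for pain response, and section 11.1 fixes a one-sided, patient-level test for re-treatment.

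**The concern.** A Pearson chi-square on a table of arm by grade treats the grades as unordered labels. With k occupied grades it has k − 1 degrees of freedom, most of them spent on patterns that objective 2.2.3 does not ask about. A trend test puts its single degree of freedom on a shift towards higher grades. If severe grades are rare, the full table is also sparse and the large-sample chi-square p-value is only approximate.

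Arm 2 receives twice the total dose of Arm 1. If the weaker test is the one relied on, a true increase in severity is more likely to be missed, and a non-significant result could be taken as reassurance. Leaving two tests open without ranking them also leaves two p-values to choose between after the data are seen.

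**Working it through.** **Inputs from the documents.** 51 patients per arm (section 11.3), equal allocation (section 4.1), grades 0 to 5 (Appendix I), and loss to follow-up of 0.2 (section 11.3), which gives 51 × 0.8 ≈ 41 per arm as a pessimistic case. The only toxicity rates are 10% versus 17% in section 1.0, for 8 Gy x 1 against 30 Gy in 10 fractions, with no grade threshold.

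**Assumptions.** Alpha 0.05, with 0.20 as a sensitivity; the grade distributions below; one worst grade per patient.

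**The plan's own figure.** The only stated power is for the primary endpoint: Φ(√(27.5/4) × |ln 0.5251| − 0.8416) = Φ(2.622 × 0.6442 − 0.8416) = Φ(0.8475) = 0.8016, against 0.80195 stated. It reproduces, but says nothing about toxicity.

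**Yes/no benchmark.** For 10% versus 17%, the pooled rate is 13.5%. The null standard error is √(2 × 0.135 × 0.865/51) = 0.0677 and the alternative one is √((0.10 × 0.90 + 0.17 × 0.83)/51) = 0.0673. Two-sided power at 0.05 is Φ((0.07 − 1.96 × 0.0677)/0.0673) ≈ 18%; one-sided it is 27%. Power is low before the choice between the two severity tests arises.

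**Tests compared.** With t_j patients at grade j over both arms, a_j and b_j of them in Arms 1 and 2, N in total and scores s_j = 0, 1, 2, …:
- Chi-square: Σ(O − E)²/E with E = t_j/2, empty grades dropped.
- Trend: Z = U/√V, where U = Σ s_j(b_j − t_j/2) and V = ¼[Σ s_j² t_j − (Σ s_j t_j)²/N].

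**Simulated power** (60,000 trials per row, 51 per arm). Ratio is chi-square power over two-sided trend power.

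| Assumed worst grade, Arm 1 vs Arm 2 (%) | Chi-square, 0.05 | Trend, 0.05 | Ratio, 0.05 | Ratio, 0.20 |
|---|---|---|---|---|
| A: grades 0–4, 60/30/7/2.5/0.5 vs 52/31/11/5/1 (grade 2+ 10 vs 17) | 9.5% | 19.2% | 0.49 | 0.75 |
| A with grades 3–4 pooled | 11.2% | 19.6% | 0.57 | 0.81 |
| A collapsed to 0–1/2/3+ | 12.4% | 17.6% | 0.70 | 0.87 |
| A collapsed to 0–1/2+ | 17.5% | 17.5% | 1.00 | 1.00 |
| B: any toxicity 10 vs 17, 90/4/4/1.5/0.5 vs 83/6.8/6.8/2.55/0.85 | 7.0% | 15.0% | 0.47 | 0.80 |
| C: Arm 1 as A, Arm 2 by proportional odds, 44.9/38.1/11.6/4.5/0.9 (grade 2+ 10 vs 17) | 20.3% | 32.9% | 0.62 | 0.81 |
| D: larger effect, Arm 1 as B, Arm 2 70/12/12/4.5/1.5 | 48.5% | 64.0% | 0.76 | 0.92 |

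Over a wider set of full-scale distributions with 10% versus 17% at grade 2 or higher, the ratio at alpha 0.05 was 0.49 to 0.73 and two-sided trend power 12% to 33%. With 41 per arm, A gives 7.7% against 16.2%, and the lowest ratio seen at 10% versus 17% was 0.40, under a distribution of type B.

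**Sparseness.** Under A, mean expected counts per arm are 51 × 9% = 4.6 at grade 2, 51 × 3.75% = 1.9 at grade 3 and 51 × 0.75% = 0.4 at grade 4. Because grade 4 is often empty and grade 2 sometimes exceeds 5, the average share of expected counts below 5 is 45% to 50%. With no true difference, the chi-square rejects about 3.4% of the time at nominal 5%; the trend test rejects about 5%.

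**Interval width.** If 10% and 17% were observed, the 95% interval for the difference is 7 ± 1.96 × 6.73 points, or about −6 to +20 points.

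**The case against.** The best defence is that section 11.2 already names the trend test for this purpose, so the loss occurs only if the chi-square alone is relied on. That is correct: the defect is an unranked pair of tests, and a reader who infers that the plan has chosen the wrong test outright goes beyond the text.

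Several other points limit the claim.
- **Table layout.** A full-grade table with four degrees of freedom is an inference. The plan gives no layout, and Appendix I allows six grades. If grades were split only at 2 or higher, the two tests coincide and nothing is lost.
- **Halved power.** A reader might infer this as a general result. It appears only with uncollapsed grades, rates near 10% versus 17% and alpha 0.05. The only alpha in the documents is one-sided 0.20, for the primary endpoint, and at 0.20 the ratios are 0.75 or higher.
- **Rates.** The section 1.0 figures are for a different comparison and carry no grade threshold.
- **Sidedness.** Setting the chi-square's 9.5% against the one-sided trend test's 29.2% under A mixes two changes. Ordering accounts for 9.5% to 19.2%; the rest comes from going one-sided, which is a preference.
- **Scope.** This is not the only planned comparison of harm, because section 11.2 also compares the number of toxicities, although it names no test for that.
- **Direction of error.** A conservative chi-square does not create false toxicity signals.
- **Remedy.** Switching tests leaves power low, so it cannot by itself prevent misreading.

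All of this bears on the size of the loss. None of it supplies the missing statement of which test decides.

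**Conclusion.** The point holds in conditional form. For an ordered outcome and a directional objective, section 11.2 commits to a test that, on a table of several grades, ignores order, and leaves the better-suited test optional and unranked.

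If the chi-square is relied on with 51 per arm, it loses roughly a quarter to more than half of the two-sided trend test's power. That rests on alpha 0.05, on 10% versus 17% toxicity borrowed from another comparison, on assumed grade distributions, and on at least three grade categories. The loss is smaller with larger effects or alpha 0.20, and absent for a two-category split. Under distribution A on the full scale, about half the expected counts fall below 5 and the chi-square is conservative, at about 3.4% for nominal 5%.

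The documents do not support saying that the plan mandates an unordered full-grade analysis, that power is halved in general, or that severity is the only harm comparison. Nor would the trend test make the comparison adequately powered.

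**What to change.** In section 11.2:
- Make an exact Cochran-Armitage trend test on each patient's worst CTCAE grade, each patient counted once, the deciding severity comparison.
- State its alpha and sidedness, the grade scores or grouping, and the assessment window for worst grade, before toxicity data are compared by arm.
- Label the chi-square descriptive.
- Report the between-arm difference in grade 2 or worse toxicity with a confidence interval, and state that a non-significant test is not evidence of no added toxicity. This matters most for interpretation, given two-sided power of about 12% to 33% at the borrowed rates.

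The cost is plan wording only: the trend test is already named, and grades are already collected in Appendix I. The statistical price is less sensitivity to differences that do not increase with grade; the descriptive chi-square and a table of grades by arm would still show those.
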